**Study Design:**

This is a Phase 2a, randomized, double-blind, placebo-controlled, parallel group, multiple arm, multicenter study of 3 different doses of HPG1860 versus placebo in subjects with biopsy-confirmed or phenotypic NASH. Screening will occur up to 5 weeks prior to randomization; all eligible subjects will have baseline hepatic imaging during Screening, prior to randomization. Approximately 80 eligible subjects will be randomized 1:1:1:1 on Day 1/Week 0 (T1) to receive either HPG1860 3 mg (n = 20), or 5 mg (n = 20), or 8 mg (n = 20), or placebo (n = 20) for 12 weeks. Following a preplanned interim analysis, a dose cohort may be dropped and/or added.

Randomized subjects will return for clinic visits at Week 2 (T2), Week 4 (T3), Week 8 (T4), and Week 12 (T5) as well as Week 16 (T6). Imaging procedures will be completed during Screening, Week 4 (T3), and Week 12 (T5). A follow-up visit will be completed 4 weeks after last dose of investigational medicinal product (IMP) at Week 16 (Visit T6).

At selected PK sites, serial PK samples will be collected from approximately 6 to 8 subjects in each dose cohort; blood samples will be collected on Day 1 pre-dose (within 30 minutes prior to dosing) and at 1, 2, 4, 6, and 8 hours ( $\pm 15$  minutes) post-dosing and on Day 14 pre-dose (within 30 minutes before dosing) and at 1, 2, 4, 6, and 8 hours ( $\pm 15$  minutes) post-dosing, and at 24 hours

(±30 minutes) prior to dosing on Day 15.

For all subjects, PK samples will be taken within 30 minutes prior to dosing at Weeks 4, 8, 12, and 16.

This study includes collection of reserve samples at Baseline (Day 1) and Week 12 for future biomarker analysis, unless prohibited by local law or regulations, and where approved by the Institutional Review Board (IRB).

**Duration of  
Treatment:**

Total study duration per subject: 21 weeks (approximate)

Screening: up to 5 weeks

Treatment: 12 weeks

Follow-up: 4 weeks

**Planned Sample Size  
and Treatment  
Groups:**

Planned: Approximately 80 adult male and female subjects

HPG1860 3 mg (n=20)

HPG1860 5 mg (n = 20)

HPG1860 8 mg (n = 20)

Placebo (n = 20)

Following a preplanned unblinded (comparative) interim analysis when 50% of randomized subjects have reached the Week 12 endpoint, an ongoing treatment group (3 mg, 5 mg, or 8 mg) may be dropped and/or a new treatment group of dose may be added.

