### **Statistical Procedures:**

#### **Sample Size**

A sample size of 17 in each group will provide 90% power to detect an absolute difference in mean CFB of 7.0% (a 33% reduction from baseline assuming a percent LFC value of 21.5% at baseline and 14.5% at Week 12) in at least 1 of the HPG1860 treatment groups compared to placebo using Dunnett's multiple comparisons test with a 2-sided significance level of 0.05 and assuming a common standard deviation of 6.8%. To account for a 15% dropout rate, approximately 20 subjects per group will be randomized.

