### **Key Secondary Efficacy Analysis**

The change in LFC measured by MRI-- PDFF from baseline to Week 12 will be analyzed using analysis of covariance (ANCOVA) adjusted for baseline LFC and treatment group. To control for multiple comparisons, Dunnett's test will be used to test if any of the treatment groups are significantly different from the placebo group.

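### Key Week 12 liver-fat test: stating Dunnett's test in step-down form would add about 7 points of power per dose if all three doses work, with any-dose power unchanged

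*Combined protocol and SAP*

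**What the plan says.** All references are to the combined protocol and SAP.

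- **Key Secondary Efficacy Analysis.** The Week 12 change in liver fat content "will be analyzed using analysis of covariance (ANCOVA) adjusted for baseline LFC and treatment group". For multiplicity, "Dunnett's test will be used to test if any of the treatment groups are significantly different from the placebo group". The text says neither single-step nor step-down.
- **Sample Size.** "A sample size of 17 in each group will provide 90% power to detect an absolute difference in mean CFB of 7.0" percentage points, with power defined as success "in at least 1 of the HPG1860 treatment groups compared to placebo". The test is "Dunnett's multiple comparisons test with a 2-sided significance level of 0.05", and the common SD is 6.8. No power is given for a particular dose or for all doses together.
- **Other Secondary Efficacy, Pharmacokinetic, and Pharmacodynamic Analyses.** The Week 4 change uses the ANCOVA of the primary efficacy analysis. I take that to mean the Week 12 liver-fat analysis, since the primary endpoint is safety.
- **Study Design, planned sample size and treatment groups.** After an unblinded interim analysis, held when half the randomized subjects have reached Week 12, "an ongoing treatment group (3 mg, 5 mg, or 8 mg) may be dropped", and a new dose group may be added.

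**The concern.** Single-step Dunnett holds every dose to the same critical value, even after another dose has already been shown to differ from placebo. The step-down (closed) form tests the largest statistic against the three-dose critical value, the next against the two-dose value, and the last against the ordinary t value. It stops at the first non-significant result. It rejects everything that single-step rejects and sometimes more, and in a fixed design it keeps the familywise error at 5%.

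The trial runs three doses and allows for changing them, so readers will want to know which doses lower liver fat as well as whether any does. With about 17 completers per arm, power for an individual dose is modest, and some of it can be recovered without more subjects.

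**Working it through.** **Inputs (Sample Size and Study Design).** Three doses and placebo, 1:1:1:1; n = 17 completers per arm; SD 6.8; effect 21.5 − 14.5 = 7.0 points; two-sided 5%; 15% dropout, so 17 / 0.85 = 20 randomized per arm.

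**Test statistics.** For dose i, t_i = (mean_i − mean_placebo) / (s·√(2/n)). The standard error is 6.8 × √(2/17) = 2.332, so a 7.0-point effect has noncentrality 7.0 / 2.332 = 3.00. The three statistics share the placebo arm (correlation 0.5). Residual df are 4 × 17 − 4 = 64, or 63 with one covariate; the choice does not change the conclusions. No correlation between baseline and follow-up is given, so the precision gain from ANCOVA is not modelled.

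**Critical values (simulated).** Three doses 2.406; two doses 2.262; one dose 1.998 (ordinary t). Single-step uses 2.406 throughout; step-down uses 2.406, 2.262 and 1.998 in order.

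**The plan's figure.** With all three doses at 7.0, simulated power for at least one dose is 90.8% at n = 17 and 88.9% at n = 16. The stated 90% with 17 per group therefore reproduces. Power for one given dose at the same cut-off (noncentral t, noncentrality 3.00) is 72.3%.

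**Single-step against step-down, n = 17, SD 6.8:**

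| True effects (points) | Power measure | Single-step | Step-down | Gain |
|---|---|---|---|---|
| 7, 7, 7 | at least one dose | 90.8% | 90.8% | 0 |
| 7, 7, 7 | each dose | 72.3% | 79.1% | 6.8 |
| 7, 7, 7 | all three doses | 50.5% | 66.3% | 15.8 |
| 7, 7, 0 | each active dose | 72.3% | 75.2% | 2.9 |
| 7, 7, 0 | both active doses | 58.9% | 64.5% | 5.6 |
| 7, 0, 0 | the active dose | 72.3% | 72.4% | 0.1 |
| 4, 6, 7 (assumed) | dose with effect 4 | 25.2% | 35.7% | 10.5 |
| 4, 6, 7 (assumed) | dose with effect 6 | 56.8% | 62.3% | 5.5 |
| 4, 6, 7 (assumed) | dose with effect 7 | 72.3% | 74.9% | 2.6 |

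**Equivalent in subjects.** Single-step power for one dose at 7.0 is 77.9% with 19 completers per arm and 80.2% with 20. Reaching 79% would therefore take 2 to 3 more completers per arm, or 8 to 12 over four arms.

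**Familywise error, fixed four arms:**

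| True effects | Single-step | Step-down |
|---|---|---|
| 0, 0, 0 | 5.0% | 5.0% |
| 0, 0, 7 | 3.5% | 4.5% |
| 0, 7, 7 | 1.9% | 3.9% |
| 0, 0, 20 | 3.5% | 5.0% |
| 0, 20, 20 | 1.9% | 5.0% |

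Repeat simulations put the 0, 7, 7 step-down figure at 3.8% to 3.9%. Step-down stays within the 5% limit and gets its power from the margin that single-step leaves unused once some doses work.

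**The case against.** The best defence is that nothing here is wrong. Dunnett's test is standard, it matches the sample-size calculation, and the stated aim of showing an effect in at least one dose gains nothing from step-down. That stands: the any-dose power is identical because the first step is the same. The plan sets no power target for individual doses, so their value is a judgement about what the trial should deliver.

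Four further points on that side have weight.

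- Single-step is inferred from the unqualified name. The inference is reasonable, and if step-down was intended the same sentence is needed to say so.
- The largest gains need all three doses to have the full planned effect. Doses of 3, 5 and 8 mg need not have equal effects.
- Single-step does buy something. Its actual error is lower when some doses work (1.9% against about 3.9% at 0, 7, 7), and its simultaneous intervals agree with its tests.
- The error rates were checked for four fixed arms. Dropping or adding a dose on unblinded data changes the comparisons, and the text gives no multiplicity rule for that. This limits the claim of 5% control, but it limits the plan's own Dunnett test equally, so it does not favour one form over the other.

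**Conclusion.** The point holds as a cheap efficiency gain on a key secondary endpoint. If every dose has the 7.0-point effect, step-down Dunnett adds about 7 points of power per dose and about 16 points for all three doses jointly. With two active doses the per-dose gain is about 3 points, with one it is negligible, and under assumed effects of 4, 6 and 7 it is about 10, 5 and 3 points. These figures assume 17 completers per arm, SD 6.8, a fixed four-arm design and no gain from the baseline covariate.

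A reader might infer three stronger things that the documents do not support.

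- That single-step costs 7 to 16 points of power for a given dose. The 16 is the joint power for all three doses. A single dose could gain that much only if its own effect were about 5 points and both other doses were certain to be significant; at an effect of 7.0 the corresponding ceiling is 11.7 points.
- That single-step gives nothing in return. The error table shows that it is more conservative when some doses work, although the plan asks only for the 5% limit.
- That step-down secures 5% in this trial as designed. Neither form does so by itself once a dose may be dropped or added at the interim.

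**What to change.** In the Key Secondary Efficacy Analysis, replace the Dunnett sentence with one to this effect: *Each dose is compared with placebo by the step-down Dunnett procedure (closed test, two-sided familywise 5%) on the ANCOVA estimates; single-step Dunnett 95% simultaneous confidence intervals are reported alongside.* Apply the same to the Week 4 ANCOVA. Leave the Sample Size power statement as it is, since its at-least-one-dose power is unchanged.

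The cost is one sentence and standard software, with no extra subjects. The downside is that a dose may be declared significant while its simultaneous interval includes zero; the plan should say in advance that the step-down result governs the test and the intervals are for estimation. Multiplicity after the interim dose drop or addition needs its own rule under either form, and this change does not supply it.

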### **Other Secondary Efficacy, Pharmacokinetic, and Pharmacodynamic Analyses**

The proportion of subjects with  $\geq 30\%$  reduction in LFC from baseline to Week 4 and Week 12 will separately be compared across treatment groups using a chi-square test.

The change in LFC measured by MRI-PDFF from baseline to Week 4 will be compared using ANCOVA as proposed for the primary efficacy analysis.

PK parameters including  $AUC_{0-\infty}$ ,  $AUC_{0-t}$ ,  $AUC_{0-24h}$ ,  $C_{max}$ ,  $T_{max}$ ,  $T_{1/2}$ ,  $CL/F$ ,  $V_z/F$ ,  $R_{ac}$ , and  $C_{trough}$  of HPG1860 in subjects with NASH will be reported by dose group and study day.

Biomarkers for liver injury and apoptosis, fibrosis, metabolism/cardiometabolic, and other biomarkers will be summarized by the value and by CFB in the value (where appropriate) at each postbaseline time point.

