### Primary Objectives and Endpoints

Objective	Endpoint

To investigate the safety and tolerability profile of HPG1860 3 mg, 5 mg, and 8 mg versus placebo in subjects with nonalcoholic steatohepatitis (NASH).

	
Primary Safety Endpoint
 
Safety and tolerability of 12 -week treatment of HPG1860 3 mg, 5 mg, and 8 mg in subjects with NASH as assessed by:
 

Treatment-emergent adverse events (TEAEs)

Adverse events of special interest (AESI)

Serious adverse events (SAEs)

Changes in clinical safety laboratory values

Vital signs

Electrocardiogram (ECG)

To evaluate the efficacy of HPG1860 compared to placebo.

	
Key Secondary Efficacy Endpoint
 

Change from baseline (CFB) in liver fat content (LFC) measured by magnetic resonance

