### Secondary Objectives and Endpoints

	
imaging-proton density fat fraction (MRI-PDFF) at Week 12
 
Other Secondary Endpoints:
 
 
Percentage of subjects with <math>\geq 30\%</math> reduction in LFC from baseline measured by MRI-PDFF at Week 4 and Week 12
 
CFB in LFC as measured by MRI-PDFF at Week 4
 

 
To evaluate the pharmacokinetic (PK) profile of HPG1860 in NASH patients
 
	
PK Endpoints including:
 
 
Area under the curve from time zero to infinity (<math>AUC_{0-\infty}</math>), AUC from time zero to the time of the last quantifiable concentration (<math>AUC_{0-t}</math>), AUC during the 24- hour dosing interval (<math>AUC_{0-24h}</math>), maximum observed concentration (<math>C_{max}</math>), time to maximum plasma concentration (<math>T_{max}</math>), half-life (<math>T_{1/2}</math>), apparent total clearance of the drug from plasma after oral administration (CL/F), and apparent volume of distribution during terminal phase after extravascular administration (<math>V_z/F</math>)
 
Trough concentration (<math>C_{trough}</math>)
 
Accumulation ratio (<math>R_{ac}</math>) based on <math>C_{max}</math> and AUC
 

 
To evaluate the effect of HPG1860 compared to placebo on biomarkers of interest
 
	
 
CFB in insulin, fasting plasma glucose (FPG) and homeostatic model assessment of insulin resistance (HOMA-IR) at Weeks 8, 12, and 16. Note:
 

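### The chi-square test planned for the 30% liver-fat responder rate names no dose-versus-placebo comparison, so its result would not answer the efficacy objective

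*Combined protocol and SAP*

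**What the plan says.** Under Other Secondary Efficacy, Pharmacokinetic, and Pharmacodynamic Analyses, the 30% responder proportions "will separately be compared across treatment groups using a chi-square test". Separately here means once for Week 4 and once for Week 12. Secondary Objectives and Endpoints lists the endpoint among the other secondary endpoints, as the percentage of subjects with at least a 30% "reduction in LFC from baseline measured by MRI-PDFF at Week 4 and Week 12".

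The efficacy objective, under Primary Objectives and Endpoints, is "To evaluate the efficacy of HPG1860 compared to placebo". Study Design gives four arms of about 20: placebo, 3 mg, 5 mg and 8 mg.

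For Week 12 LFC change, Key Secondary Efficacy Analysis uses ANCOVA with Dunnett's test against placebo. Week 4 LFC change refers back to the same ANCOVA. For the responder endpoint the text gives no table layout, degrees of freedom, contrast, effect estimate, confidence interval or multiplicity rule.

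**The concern.** A chi-square test across four arms has the null hypothesis that all four response rates are equal. Rejecting it says only that some arms differ. The difference may lie between two doses, or a dose may do worse than placebo. Neither supports a statement about efficacy against placebo, yet a single significant p-value on a responder endpoint is easily reported that way.

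The test also produces no estimate. A Phase 2a trial of three doses, in which a dose may be dropped or added after an interim analysis, needs the response rate of each dose relative to placebo and its uncertainty. LFC change has comparisons with placebo; the responder version of the same measurement has none stated.

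**Working it through.** **The plan's own figure.** Sample Size states: "A sample size of 17 in each group will provide 90% power", for an "absolute difference in mean CFB of 7.0" percentage points, "assuming a common standard deviation of 6.8" points, using Dunnett's test at two-sided 0.05. A simulation of Dunnett's test (64 degrees of freedom, critical value 2.406) gives 90.8% power at 17 per arm for at least one significant dose when all three doses have the 7.0-point effect (88.9% at 16 per arm). With 15% dropout, 17/0.85 = 20. The figure reproduces, but it concerns LFC change. The plan gives no power or response rates for the responder endpoint.

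**A significant four-arm test with no dose separating from placebo.** Take 20 per arm and responders 5 (placebo), 1 (3 mg), 9 (5 mg), 5 (8 mg). The total is 20 of 80, so each arm expects 5 responders and 15 non-responders.

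- Four-arm chi-square: (0 + 16 + 16 + 0)/5 + (0 + 16 + 16 + 0)/15 = 6.40 + 2.13 = 8.53, 3 df, p = 0.036. All of it comes from the 3 mg and 5 mg arms.
- 3 mg v placebo: 40 × (5×19 − 15×1)² / (20×20×6×34) = 3.14, p = 0.077, with the dose worse than placebo. Fisher p = 0.18.
- 5 mg v placebo: 40 × (5×11 − 15×9)² / (20×20×14×26) = 1.76, p = 0.185. Fisher p = 0.32.
- 8 mg v placebo: identical counts, p = 1.00 by either test.

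**How often this might happen.** Response rates must be assumed. Sample Size works from "assuming a percent LFC value of 21.5% at baseline and 14.5% at Week 12". Suppose every subject starts at 21.5%, changes are normal with SD 6.8, and placebo does not change on average. A 30% fall is 0.30 × 21.5 = 6.45 points. Then:

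- placebo: P(Z > 6.45/6.8) = P(Z > 0.949) = 17%
- active dose: P(Z > (6.45 − 7.0)/6.8) = P(Z > −0.081) = 53%

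With only the top dose active (17/17/17/53%) and 17 per arm, about 17% of significant four-arm results come with no dose better than placebo even at unadjusted two-sided 0.05. At a Dunnett-type cut-off of 2.349 the share is about 32%.

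**Dose order.** Responders 3, 5, 7 and 9 of 17 give chi-square 5.15, p = 0.161, for all 24 orderings of the arms. The Cochran-Armitage trend test in dose order gives p = 0.023.

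**Power under different dose-response shapes.** Binomial simulation, two-sided 0.05, rates in the order placebo/3/5/8 mg. The pairwise column counts at least one dose better than placebo at the 2.349 cut-off. Trend scores are 0/3/5/8.

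| Assumed rates | n per arm | Four-arm | Pairwise | Trend |
|---|---|---|---|---|
| 17/53/53/53% | 17 | 61% | 74% | 55% |
| 17/29/41/53% | 17 | 47% | 53% | 66% |
| 17/17/17/53% | 17 | 67% | 47% | about 65% |
| 10/20/35/50% | 20 | 73% | 77% | 87% |

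Two further shapes at 20 per arm, four-arm v trend: plateau 10/50/50/50%, 84% v 75%; only the middle dose active 10/10/50/10%, 89% v 6%. No method is best throughout. Nor does Fisher's test per dose always help. For 10/20/35/50% at 20 per arm, the chance that at least one dose is significant is 78% unadjusted and 59% with Bonferroni, against 73% for the four-arm test.

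**The case against.** The text does not state a 4x2 table, so pairwise chi-square tests cannot be excluded. That stands: the four-arm test is the natural reading, not an explicit statement. It does not remove the problem, because under the pairwise reading nothing controls multiplicity. With equal true rates of 10% to 17% and 17 to 20 per arm, three unadjusted comparisons give roughly an 8% to 12% chance of at least one false positive per visit.

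The consequence is small. The primary endpoint is safety, the responder rate is a dichotomised form of LFC, LFC change is compared with placebo, and no decision in the plan is tied to the responder p-value. This also stands, and it limits the weight of the point.

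The 5/1/9/5 table was chosen to illustrate. That is fair: it shows what can happen, not how often. The 17% and 32% shares address frequency, but only for one assumed scenario.

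A reader might infer that the four-arm test is the weaker test and that a trend test should replace it. The documents do not support that. They assume no monotone dose response and allow doses to be dropped or added. Under a plateau or a single active middle dose, the four-arm test has more power than the trend test.

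**Conclusion.** The point holds as one of interpretability and specification. As most naturally read, the planned test does not answer the objective of comparing HPG1860 with placebo, provides no dose-placebo estimate, and is out of line with the plan's treatment of LFC change. Under the other reading, the comparison and its multiplicity control are unstated. Either way the text should be changed.

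The arithmetic of the example table is exact. The frequencies and powers rest on assumed response rates; the 17% and 53% also assume a common baseline, normal changes and no mean change on placebo.

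Two stronger conclusions might be drawn and are not supported. The four-arm test is not invalid: with equal true rates of 10% or 17% its simulated false-positive rate is 4% to 5%. Nor is the trial's main efficacy conclusion undermined, since that rests on the Dunnett comparisons of LFC change. This is a correction that should be made to a non-key endpoint.

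**What to change.** At each of Week 4 and Week 12, define the analysis as each dose versus placebo. Report the risk difference with a 95% confidence interval, and test with an exact test or with logistic regression adjusted for baseline LFC. Say whether the p-values are multiplicity-adjusted, in keeping with the key secondary analysis, or descriptive.

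A Cochran-Armitage trend test may be added as supportive only, scored on the doses actually studied so that it remains defined if an arm is dropped or added.

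The cost is wording, with no added subjects, visits or scans. There are two statistical downsides. There are more p-values: 3 per visit × 2 visits = 6 instead of 2, or 8 with a trend test at each visit. Power is also lower than the four-arm test's if only one dose works: about 47% v 67% at 17 per arm, with assumed rates 17/17/17/53% and the Dunnett-type cut-off. How missing scans are counted is a separate question and is not part of this change.

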	
FPG and insulin will be measured as clinical safety laboratory assessments
 
 
• CFB in alanine aminotransferase (ALT), aspartate aminotransferase (AST), gamma-glutamyl transferase (GGT) at Weeks 12 and 16. Note: ALT, AST, and GGT will be measured as clinical safety laboratory assessments
 
• CFB in non-invasive biomarkers of liver injury and apoptosis: cytokeratin-18 (CK-18; M30 and M65 fractions), fibrosis-4 (FIB-4), AST to platelet ratio index (APRI), and N-terminal propeptide of type III collagen (Pro-C3) at Weeks 12 and 16
 
• CFB in enhanced liver fibrosis (ELF), a non-invasive biomarker of fibrosis, hyaluronic acid, procollagen III N-terminal peptide (PIIINP) and tissue inhibitor of metalloproteinase-1 (TIMP-1) at Weeks 12 and 16
 
• CFB in pharmacodynamic (PD) and cardiometabolic biomarkers: high-sensitivity C reactive protein (hs-CRP), 7<math>\alpha</math>-hydroxy-4-cholesten-3-one (C4), alkaline phosphatase (ALP), total bile acids (BAs), non-high density lipoprotein cholesterol (non-HDL-C), low-density lipoprotein cholesterol (LDL-C), total
 

--	--

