- Phenotypic diagnosis based on the following: liver stiffness  $\geq 8.0 \text{ kPa}$  and controlled attenuation parameter (CAP)  $> 300 \text{ dB/m}$  on transient elastography (TE) OR

- Elevated ALT (males >40 IU/L, females >30 IU/L), BMI  $\geq 27$  kg/m^2, and diagnosis of type 2 diabetes mellitus (T2DM).
7. Subjects will have CAP >300 dB/m on TE at screening and hepatic fat assessed by a central reader of MRI-PDFF  $\geq 10\%$  during Screening.
  8. Male subjects must refrain from sperm donation from Screening through at least 90 days following the last dose of IMPs.
  9. Female subjects must refrain from egg donation or harvest for 30 days after last dose of IMPs.
  10. Willing and able to adhere to study restrictions and agree to comply with study protocol.

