#### **Primary Safety Analysis**

Descriptive statistics will be used to assess the safety and tolerability

of 12-week treatment of HPG1860 3 mg, 5 mg, and 8 mg in subjects with NASH during the study. Safety assessments will include TEAEs including TEAEs of special interest, SAEs, changes in clinical safety laboratory values, 12-lead ECGs, and vital signs.

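### The biomarker objective is a comparison with placebo, but the plan only summarizes values and changes, so no placebo-adjusted estimate or interval is planned for any biomarker under that objective

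*Combined protocol and SAP*

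**What the plan says.** Secondary Objectives and Endpoints states the aim as "To evaluate the effect of HPG1860 compared to placebo on biomarkers of interest" and lists change-from-baseline endpoints at fixed weeks.

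The analysis of these endpoints is in Other Secondary Efficacy, Pharmacokinetic, and Pharmacodynamic Analyses. It says that the biomarkers "will be summarized by the value and by CFB in the value (where appropriate) at each postbaseline time point". No model, contrast, interval or test is named.

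The same section treats the LFC endpoints differently. The responder proportions "will separately be compared across treatment groups using a chi-square test", and "The change in LFC measured by MRI-PDFF from baseline to Week 4 will be compared using ANCOVA". For Week 12, Key Secondary Efficacy Analysis says that the change in LFC "will be analyzed using analysis of covariance (ANCOVA) adjusted for baseline LFC and treatment group", with Dunnett's test against placebo.

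Some biomarkers are also safety laboratory tests. For example, "ALT, AST, and GGT will be measured as clinical safety laboratory assessments". The safety route is descriptive as well: "Descriptive statistics will be used to assess the safety and tolerability" (Primary Safety Analysis).

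**The concern.** An objective about an effect relative to placebo needs an estimate relative to placebo. Summaries of values and changes do not give one. A reader could subtract one group's mean change from another's, but would have no interval and no adjustment for baseline imbalance, with about 20 subjects randomized per group.

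Change from baseline alone can also include shifts that are not drug effect. ALT is the clearest case in this protocol. One of the three ways to meet the NASH definition includes "Elevated ALT (males >40 IU/L, females >30 IU/L"), so subjects who entered that way were partly selected on a high reading and may fall back with no treatment effect.

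At stake is how the dose groups are read on markers that the plan itself classes as pharmacodynamic and cardiometabolic, such as C4, ALP, total bile acids and LDL-C, in a study of three doses.

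**Working it through.** **1. Is a biomarker contrast planned anywhere in the supplied text?**

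- Other Secondary Efficacy, Pharmacokinetic, and Pharmacodynamic Analyses: summary only for biomarkers; comparisons only for LFC.
- Key Secondary Efficacy Analysis: ANCOVA and Dunnett, for Week 12 LFC only.
- Primary Safety Analysis: descriptive, so it supplies no contrast for the markers that double as safety tests.
- Exploratory Analyses: metabolites and PK correlations, with LFC the only outcome named.

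None of them supplies one.

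**2. The plan's own figure.** No figure is given for the biomarkers. The LFC sample size (difference 7.0, SD 6.8, two-sided Dunnett at 0.05, 17 per group) reproduces. Simulation gives 90.8% power for at least one dose if all three doses have the 7.0 effect, and 17 / 0.85 = 20 per group after 15% dropout. I use 17 and 20 per arm below.

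**3. How many contrasts the objective implies**, from the listed endpoints and weeks:

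| Group | Markers | Visits | Marker-visits |
|---|---|---|---|
| Insulin, FPG, HOMA-IR | 3 | 3 | 9 |
| ALT, AST, GGT | 3 | 2 | 6 |
| CK-18 M30 and M65, FIB-4, APRI, Pro-C3 | 5 | 2 | 10 |
| ELF, hyaluronic acid, PIIINP, TIMP-1 | 4 | 2 | 8 |
| hs-CRP, C4, ALP, bile acids, non-HDL-C, LDL-C, TC, apoB | 8 | 5 | 40 |
| Total | 23 | | 73 |

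Three doses give 3 × 73 = 219 contrasts. Every marker is measured at Week 16, so the on-treatment visits give 73 − 23 = 50 marker-visits and 3 × 50 = 150 contrasts. With no effect anywhere, the expected number of nominal 95% intervals that exclude no effect is 0.05 × 219 = 10.95, or 0.05 × 150 = 7.5 on treatment.

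**4. Precision of each contrast.** In units of the SD of the change, the half-width is t(0.975, df) × √(2/n), with df = 4(n − 1):

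- n = 17: df = 64, 1.998 × 0.343 = 0.69.
- n = 20: df = 76, 1.992 × 0.316 = 0.63.

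Baseline adjustment narrows these. Assuming equal variance at baseline and follow-up and correlation ρ between them, the variance of the ANCOVA contrast relative to a difference in changes is (1 − ρ²) / [2(1 − ρ)] = (1 + ρ)/2. The documents give no ρ. For assumed values:

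- ρ = 0.5: ratio 0.75, √0.75 = 0.866, so half-widths of 0.59 (n = 17) and 0.55 (n = 20).
- ρ = 0.7: ratio 0.85, √0.85 = 0.922, so half-widths of 0.63 and 0.58.

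**5. Regression to the mean in ALT.** The expected fall in an arm is roughly f × (1 − r) × d. Here f is the fraction selected on ALT, r the test-retest correlation and d the distance of their screening mean above the population mean. The documents give none of the three. With assumed d = 1 SD and r = 0.7 to 0.8, the fall is 0.3 to 0.2 SD among those subjects, and f times that in the arm. If baseline is a Day 1 sample separate from Screening, part of it happens before baseline. The direction is plausible, but the size cannot be derived.

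**The case against.** Descriptive reporting of many biomarkers is a common and defensible choice in a small phase 2a study whose primary endpoint is safety. The switch from comparison for LFC to summary for biomarkers looks deliberate. Randomization makes regression to the mean equal across arms in expectation, so if the summaries are shown by group, placebo is there to compare against. The supplied text is also a synopsis, and a fuller statistical section, if there is one, could not be checked. All of this stands, but it does not remove the mismatch: the objective says comparison and the analysis gives none.

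Stronger readings that the documents do not support:

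- *That the trial cannot answer its biomarker question.* The randomized data allow the contrast with no design change; what is missing is the planned estimate and its interval.
- *That regression to the mean affects the biomarkers generally.* Elevated ALT is part of one of three alternative routes, where it is joined with BMI and type 2 diabetes. No criterion selects on C4. For ALP the only criterion is an upper exclusion limit, and LDL-C has one for subjects on stable statin or PCSK9 therapy; neither selects high values. APRI is built on AST, and no route requires raised AST.
- *That the plan prescribes raw mean changes within each arm, distorted by skewed markers.* The biomarker sentence names neither a grouping nor a statistic, and the documents say nothing about the markers' distributions.

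**Conclusion.** The point holds as a mismatch between a comparative objective and a descriptive analysis. In the supplied text, no placebo-adjusted estimate or measure of uncertainty is planned for any of the 23 biomarkers under that objective, while the plan already specifies a suitable model for LFC. This conclusion rests on the wording alone and depends on no assumed figure.

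The effect on interpretation cannot be sized from the documents. What can be sized is the remedy: a usable but imprecise contrast, with a half-width of about 0.69 to 0.63 SD of the change at 17 to 20 per arm before baseline adjustment. That assumes a common SD across arms and no missing biomarker values beyond the planned dropout. Limited precision is a reason to show intervals, not to leave out the estimate.

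**What to change.** In Other Secondary Efficacy, Pharmacokinetic, and Pharmacodynamic Analyses, keep the summaries, state that they are by treatment group, and add the following.

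- For each listed biomarker and scheduled visit, fit the ANCOVA form already planned for LFC, with treatment group and that biomarker's own baseline. A separate model per visit is enough; the plan has no repeated-measures model for LFC to carry over.
- Report each dose minus placebo with a nominal 95% confidence interval.
- Where the pooled, blinded distribution is skewed, analyze on the log scale and report ratios to placebo. Fix this choice before any unblinding, including the planned interim analysis.
- Label Week 16 as off-treatment, since it falls 4 weeks after the last dose.
- State that the intervals are exploratory and carry no multiplicity-controlled claim.

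If the sponsor wants description only, rewording the objective as descriptive would also remove the mismatch, but would give up the comparison.

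The cost is SAP wording and extra tables, with no new data and no change in sample size. The downside is about 219 nominal intervals, of which about 11 would be expected to exclude no effect by chance alone, so isolated findings must not be presented as evidence of effect.
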